activity entered into a diary. Upon completion of the Baseline Period, subjects who qualify for the study will be randomized (1:1) in a double-blind manner to receive ZX008 (at a dose of 0.5 mg/kg/day; maximum dose 20 mg/day) or placebo. Randomization will be stratified by age group (< 6 years, ≥ 6 years) to ensure balance across treatment arms, and at least 40% of subjects will be in each age group. Titration will occur in 3 steps starting with a 0.2 mg/kg/day dose of ZX008 (or placebo equivalent) on Study Days 1-7, increased to a dose of 0.4 mg/kg/day on Study Days 8-14, and then increased to a dose of 0.5 mg/kg/day on Study Days 15-21. The duration of the Titration Period is 21 days, and the maximum daily dose at any point is 20 mg/day. Following titration, subjects will continue treatment with the assigned dose of ZX008 0.5 mg/kg/day or placebo over a 12-week Maintenance Period. Total treatment time from the beginning of the Titration Period through the end of the Maintenance Period is a maximum of 15 weeks. At the end of the Maintenance Period (or early discontinuation), all subjects will enter either a taper or transition period based on whether they exit the study or are enrolled in the separate long-term open-label extension trial, respectively. PK samples will be collected during the Follow-Up visit for subjects who will be entering the open-label extension. A follow-up ECG and ECHO will be performed 3-6 months after study drug discontinuation for early termination, or for those subjects who complete the study but do not enter the open-label extension trial Cohort 2 only).

Parents/caregivers of subjects in Cohort 2 will use a diary daily to record the number/type of seizures, dosing, and use of rescue medication. A schedule of assessments is provided in [Table 2](#).

External Individuals and Committees: The ZX008 clinical program will employ an Independent Data and Safety Monitoring Committee (IDSMC) that will be responsible for safety oversight. A separate International Pediatric Cardiology Advisory Board (IP CAB) will monitor the cardiac safety of the ZX008 clinical trials. ECGs and Doppler ECHOs will be centrally read (Biomedical Systems, Inc.) and interpreted under blinded conditions using pre-specified criteria, and if necessary, with review by the IP CAB. The IDSMC will be informed of the dose selected for Cohort 2.

Number of Subjects:

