topiramate, levetiracetam, and STP. STP (together with CLB and VPA), the only drug specifically approved for this indication, is widely prescribed by pediatric epilepsy physicians for their patients with Dravet syndrome. STP is a potent inhibitor of several CYP450 isoenzymes, including CYP2D6, and when used in combination with other antiepileptic medications may increase their plasma levels and hence increase side effects. Acknowledging that an adjunctive antiepilepsy medication marketed in Europe is likely to be taken by patients also taking STP, and that inhibition of CYP2D6 is likely to increase levels of ZX008, this study focuses first on evaluating the PK and safety profile of low doses of ZX008 when administered with a standard treatment regimen (CLB + VPA or CBA + VPA + STP) in one cohort, thus establishing the dose of ZX008 that produces serum levels when given with STP that are similar to effective doses from the Belgian experiment ([Ceulemans 2012](#)). Based on data from 13 patients in Cohort 1, and data from Study ZX008-1505 the 0.5 mg/kg/day (maximum 20 mg/day) ZX008 dose was determined as the target dose for the second cohort based on matching the exposure (AUC) of fenfluramine at 0.8 mg/kg/day (maximum 30 mg/day) without STP/CLB/VLP. The analysis leveraged physiologically-based pharmacokinetics (PBPK) models for ZX008, CLB, VLP, and STP. PK and safety data from Cohort 1, and data from Study ZX008-1505 were evaluated using the model to quantify the extent of the PK interaction between fenfluramine and the combination of CBA + VPA + STP. The 0.5 mg/kg/day ZX008 dose (maximum 20 mg/day) for Cohort 2 was selected with the goal of maintaining mean patient PK exposures within 10% of that which is expected in patients receiving 0.8 mg/kg (maximum 30 mg/day) in the absence of interacting AEDs. Data from Study ZX008-1505 showed that fenfluramine does not have a significant effect on the PK of the concomitant medications (STP/CLB/VLP).

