5.5.7 Cohort 2: Transition Period

Subjects who complete the Maintenance Period and will be continuing into the open-label extension trial will be transitioned from double-blind study medication to open-label ZX008 (depicted in [Table 7](#)). Study medication will be administered as equal doses BID in the morning and in the evening approximately 12 hours apart, with food. Each dose should be separated by a minimum of 8 hours and a maximum of 12 hours. A missed dose of study medication may be taken later up to 8 hours before the next scheduled dose; otherwise, the missed dose should not be given. Study medication will be administered using the oral dosing syringe provided.

This transition is required in order to maintain the blind. All subjects entering the open-label extension trial will be transitioned from their blinded daily dose (placebo, or 0.5 mg/kg/day [maximum 20 mg/day] dose of ZX008) to the 0.2 mg/kg/day ZX008 dose during the interval between Visits 12 and 13, without breaking the blind. Subjects in the ZX008 arm will transition to 0.4 mg/kg/day dose on Days 1-7, and then transition to a dose of 0.2 mg/kg/day on Days 8-14 during the transition period. Subjects in the placebo arm will have a titration step from placebo to 0.2 mg/kg/day and then will commence taking study medication as per the open-label extension trial (0.2 mg/kg/day). All subjects will receive ZX008 0.2 mg/kg/day for the last transition step in their respective dose group. A new bottle of IMP will be started by the subject at each level of the transition step. See [Section 5.6](#) for more information about the volume of ZX008 or placebo to be administered.

Table 7. Transition Algorithm

Randomized Dose Selected for Cohort 2	Step 1 Days 1-7 after study completion	Step 2 Days 8-14 after study completion
ZX008 0.5 mg/kg/day	ZX008 0.4 mg/kg/day	ZX008 0.2 mg/kg/day
Placebo	Placebo	ZX008 0.2 mg/kg/day

Note: maximum daily dose of ZX008 is 20 mg

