6.2.5.4 Clinic Visit 6 (Maintenance Period: Day 22)

Subjects will report to the clinic in the morning on Maintenance Period Day 22. Subjects should not take their morning dose(s) of AED medication prior to reporting to the clinic. The following procedures will be performed:

- Review current seizure activity (number/type/duration) from diary since previous visit
- Record concomitant medications
- Abbreviated physical examination, including height and weight, and calculation of BMI
- Abbreviated neurological examination
- Vital signs (blood pressure, heart rate, temperature, and respiratory rate)
- Urine pregnancy test for females of child-bearing potential
- Laboratory evaluation (serum chemistry and hematology, and urinalysis)
- Urine THC panel
- Whole blood CBD
- Collect plasma sample for background AED PK evaluation prior to the morning dose of study medication(s)
- Collect and review diary with parent/caregiver
- Administer sleep quality and mealtime behavior questions
- Administer Karolinska Sleepiness Scale ([Appendix 8](#))
- Dispense diary
- C-SSRS Children's Since Last Visit Assessment ([Appendix 2](#))
- CGI-I (assessed by parent/caregiver)
- CGI-I (assessed by investigator)
- Record AEs
- Record AESI
- Collect used, partially used and unused study medication; perform drug accountability and review with parent/caregiver
- Dispense study medication

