6.2.5.11 Follow-up Visit (Clinic Visit 13; Day 120)

Subjects will report to the clinic in the morning of Visit 13. Subjects should not take their last dose of study medication or morning dose of antiepileptic medication prior to reporting to the clinic so that 4 blood samples can be obtained for steady-state PK.

For subjects entering the open-label extension trial, the subject will visit the clinic on Visit 13 (Day 120). The following will be recorded/Performed and the subject will immediately be enrolled in that separate study:

- Review current seizure activity (number/type/duration) from diary since previous visit
- AEs
- AESI
- Concomitant medications
- Collect used, partially used and unused study medication; perform drug accountability and review with parent/caregiver
- Collect plasma sample for ZX008 PK evaluation prior to the morning dose of study (last dose of Protocol 1504 study medication) and their usual AED medication(s)
- Collect additional plasma samples for ZX008 PK evaluation at 1, 2, and 4-6 hours post-dose

If the subject does not enter the open-label extension trial (or discontinues from the study early), the subject will visit the clinic on Visit 13 (Day 120) (or 14 days after the day of discontinuation). The following will be recorded/Performed:

- Review current seizure activity (number/type/duration) from diary since previous visit
- AEs
- AESI
- Concomitant medications
- Collect used, partially used and unused study medication; perform drug accountability and review with parent/caregiver

6.2.6 CARDIAC FOLLOW-UP VISIT (COHORT 1: CLINIC VISITS 18, 19/COHORT 2: CLINIC VISIT 14; 3-6 MONTHS AFTER LAST DOSE OF STUDY MEDICATION)

If the subject completes the study but does not enter the open-label extension trial or discontinues from the study early, the subject will return to the clinic for follow-up cardiac testing (ECHO, ECG, and in some cases physical examination). The timing and frequency of exams are presented in [Table 10](#). Subjects on blinded medication who are found to have been on placebo are not required to participate in follow-up testing once the blind is broken at the end of the study. As the ECHO and ECG will be administered in a separate clinic from the pediatric neurology clinic, an asymptomatic subject receiving a second follow-up ECHO and ECG does not require a physical examination.

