7.4 PHARMACOKINETIC ASSESSMENTS

Cohort 1: Blood samples for PK assessments of fenfluramine and its metabolite (norfenfluramine), CLB and its metabolite N-CLB, STP, and VPA will be obtained from all subjects via an indwelling catheter. Prior to obtaining the PK sample, about 0.5 mL should be drawn off and discarded. Samples will be collected within one hour prior to dosing (pre-dose), and at 2, 4, 8, 12, and 24-36 hours post-dose. Six samples (one pre-dose and five post-dose) will be collected from each subject for a total of approximately 27 mL.

Cohort 2: Blood samples for PK assessment (2 mL) of fenfluramine and its metabolite (norfenfluramine) will be obtained at the following time points:

- Visit 13: within 1 hour prior to the morning dose, and 1, 2, and 4-6 hours after the morning dose.

A total of 4 PK samples will be drawn for each subject for a total of approximately 8 mL of blood.

When blood draws for PK coincide with other assessments, the PK draws take precedence.

The procedure for the collection and handling of PK samples is outlined in a separate study manual.

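### All planned Cohort 2 ZX008 PK samples fall on the transition dose, so exposure at the tested 0.5 mg/kg/day is reached only by model extrapolation

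*Protocol*

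**What the plan says.** **When ZX008 is sampled.** Protocol Section 7.4 gives one occasion for Cohort 2: "Visit 13: within 1 hour prior to the morning dose, and 1, 2, and 4-6 hours after the morning dose". It adds: "A total of 4 PK samples will be drawn for each subject for a total of approximately 8 mL of blood". Section 6.2.5.11 describes the purpose as "so that 4 blood samples can be obtained for steady-state PK".

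**Who is sampled.** The synopsis states: "PK samples will be collected during the Follow-Up visit for subjects who will be entering the open-label extension". Table 2, footnote f, and the SAP schedule of assessments say the same. Children who taper take no study drug in the last six days of the taper (Section 5.5.5), and no ZX008 sample is listed for them.

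**The dose at that time.** Under Section 5.5.7 the active arm "will transition to 0.4 mg/kg/day dose on Days 1-7, and then transition to a dose of 0.2 mg/kg/day on Days 8-14". The section also says: "All subjects will receive ZX008 0.2 mg/kg/day for the last transition step in their respective dose group".

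**What the tested dose rests on.** Section 3.5 says that 0.5 mg/kg/day (maximum 20 mg/day) was chosen "with the goal of maintaining mean patient PK exposures within 10% of that which is expected in patients receiving 0.8 mg/kg" (maximum 30 mg/day) without interacting AEDs. The same section bases the expected safety profile on the predicted exposures.

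**Plasma drawn on the randomised dose.** Table 2, footnote g, schedules plasma for background AEDs at Visits 3, 6, 8 and 12. Under Section 7.2.6, Visit 6 samples are analysed after collection as a safety measure and the others at study end.

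**The concern.** The tested dose was picked by prediction. The paediatric data behind it were single doses in 13 Cohort 1 children. Ten of them were in Regimen 3, which gave 0.2 mg/kg with stiripentol, clobazam and valproate. The simulations gave every child the same stiripentol and clobazam doses (Section 3.5). Cohort 2 is where children on stiripentol take 0.5 mg/kg/day repeatedly, so it is the natural place to see whether predicted exposure is reached. Section 10.5.3 intends the Cohort 2 data to test how well the model predicts multiple dosing, but the planned samples test it only at the transition dose.

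The 20 mg/day cap was itself part of the exposure match, intended to prevent excursions in older patients. At the transition dose it hardly ever applies.

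At stake are a direct check of the dose-matching argument and the means to relate exposure at the tested dose to response or cardiac findings.

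**Working it through.** **1. Is any ZX008 sample planned outside Visit 13?** Inputs are from Protocol Table 12.

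- ZX008 PK volume: 4 × 2 mL = 8 mL, which is the stated total.
- Visit 13 volume: 8 + 4 × 0.5 mL catheter flush = 10 mL, as stated.
- Whole study: 20.7 + 4 × 17.7 + 15.7 + 10 = 117.2 mL, as stated.

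The ZX008 allowance is fully used at Visit 13, so the blood budget holds no ZX008 sample on the maintenance dose.

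**2. Which dose applies at Visit 13?** Visit 12 is Day 106 and Visit 13 is Day 120 (Table 9), each ± 4 days.

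- Nominal: 120 − 106 = transition Day 14, so 0.2 mg/kg/day by Table 7.
- Windows: the shortest interval is 116 − 110 = 6 days and the longest is 124 − 102 = 22 days. I assume that children stay on the last step if the interval exceeds 14 days.
- Of the 9 × 9 = 81 day combinations, 78 have reached 0.2 mg/kg/day. Three (intervals of 6 or 7 days) are still on 0.4. None is on 0.5. These are counts of combinations, not probabilities.

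**3. How far is the extrapolation in daily dose?** Daily dose = min(dose per kg × weight, 20 mg). The cap binds above 20/0.5 = 40 kg at the tested dose, but only above 20/0.2 = 100 kg at the transition dose.

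| Weight (kg) | Tested dose (mg/day) | Dose at Visit 13 (mg/day) | Ratio |
|---|---|---|---|
| 20 | 10 | 4 | 2.5 |
| 40 | 20 | 8 | 2.5 |
| 50 | 20 | 10 | 2.0 |
| 60 | 20 | 12 | 1.7 |

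**4. Are the samples near steady state for the transition dose?** The documents give no half-life, so I assume 12 to 48 hours with first-order, linear kinetics. At the nominal pre-dose sample the active arm has had 6 days (144 h) on 0.2 mg/kg/day, after 7 days (168 h) on 0.4. With half-life h, the level relative to 0.2 mg/kg/day steady state is

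1 + [(0.2 + 0.1 × 2^(−168/h)) / 0.2] × 2^(−144/h).

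- h = 12: 1.00. h = 24: 1.02. h = 48: 1.13.
- Multiplying by 0.2/0.5 gives 40% to 45% of the 0.5 mg/kg/day level in uncapped children.
- Former placebo children under Protocol Table 7: 1 − 2^(−144/h), or 88% to 100% of steady state. Under SAP Table 4, with 13 days (312 h) on drug: 99% to 100%.

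The two documents give the placebo arm different treatment in transition Days 1–7, and so different histories before the same samples. These tables must be reconciled.

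**5. What plasma exists on the tested dose?** With about 45 ZX008 children, Visits 8 and 12 give 45 × 2 = 90 samples at most, and Visit 6 brings this to 45 × 3 = 135. Visit 13 gives up to 45 × 4 = 180 values in that arm and 90 × 4 = 360 across both arms.

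**The case against.** The strongest reply is that the PK objective is to model single and multiple dosing, and the Visit 13 samples serve it. They are timed four-point profiles at a known dose under stiripentol, from both arms. Clearance estimated there can predict exposure at 0.5 mg/kg/day. The model also pools Cohort 1, in which Regimen 3 gave single 0.2 mg/kg doses with stiripentol, close to the 0.25 mg/kg taken at each of two daily doses in Cohort 2. The 10% figure is a dose-selection goal and not a Cohort 2 hypothesis, and no exposure-response analysis is an objective. Most of this stands. What remains is that accumulation on repeated dosing at 0.5 mg/kg/day is inferred under proportionality, and the capped dose is hardly observed.

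Objections to reusing the AED plasma also carry weight:

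- Cohort 1 used 4 mL to assay ZX008 with the AEDs. The Cohort 2 AED sample is 2 mL, and nothing shows that enough plasma is left over.
- Only Visit 8 (Section 6.2.5.6) clearly tells families to hold study medication. Visit 6 holds AEDs only, and the Visit 12 text gives no holding instruction. The procedure line that places sampling before study medication also appears at Visit 3, before any has been dispensed, so it is weak evidence of a ZX008 trough.
- Visit 6 plasma is used soon after collection.

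A reader might infer that exposure at the tested dose can never be measured, or that children who stop early can contribute no ZX008 PK. The documents do not support either. Section 8.9 asks for a ZX008 sample after a serious adverse event once dosing has begun, and Section 4.8 lets early stoppers enter the extension case by case.

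**Conclusion.** The point holds as a limitation of the PK sampling plan. No scheduled sample measures ZX008 at 0.5 mg/kg/day. The exposure match is open only to an indirect check, over a 2.5-fold range of daily dose up to 40 kg and a smaller one above. That check assumes dose-proportional kinetics under stiripentol. The PK analysis plan and the separate Cohort 2 PK report were not available, so further model checks may be specified there.

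Two stronger inferences fail. First, the steady-state label is not shown to be wrong: under the assumed half-lives the samples are close to steady state, but for the transition dose and not the tested one. Second, the efficacy conclusions are not weakened. The primary and key secondary analyses compare randomised groups and use no concentration data. No planned safety analysis uses it either. This is an inexpensive improvement worth making, not an error that threatens the trial.

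**What to change.** Where residual volume, assay stability and consent allow, assay fenfluramine and norfenfluramine in the ZX008-arm plasma collected for background AEDs at Visits 8 and 12, which Section 7.2.6 already leaves for analysis at study end. Add Visit 6 if an aliquot is retained after its safety analysis. Run the assays after unblinding.

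Record the times of the last ZX008 dose and of each draw. Enter the values in the Section 10.5.3 population PK model as timed sparse samples, not as assumed troughs. They supplement the Visit 13 profiles and do not replace them. Visit 12 is also the early-termination visit, so some children who stop early could contribute. It would also help to label the Visit 13 concentration tables (SAP Section 6.5) with the dose at sampling.

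The yield is at most about 90 values, or about 135 with Visit 6, before dropout and missed samples. The cost is the extra assays plus a check of the laboratory manual and consent, with no new visit or blood draw. Some samples may prove unusable because of volume or timing.

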6.3 ESTIMATED BLOOD VOLUME COLLECTION

The maximum total blood volume collected during the first 15 days of the study for Cohort 1 will be approximately 63.4 mL for the PK portion of the study, as outlined in [Table 11](#). The maximum total blood volume collected during the transition period of the study for Cohort 1 will be approximately 122.1 mL over 24 weeks.

Table 11. Estimated Blood Volume Collection for Cohort 1

Assessment	Screening (Day -14 to -1)	Day 1-2	Day 15	Total Screening- Day 15	Transition Period Days 43, 71, 99, 127, 155, 183
Clinical chemistry & prolactin	2 x 5 mL	--	--	10 mL	6 x 10 mL
LH, FSH, estradiol, testosterone	1 x 4 mL			4 mL	3 x 4 mL (every 8 weeks)
Hematology	2 x 2mL			4 mL	6 x 2mL
Epilepsy Genotyping	5 mL			5 mL	--
IGF-1, GH	1 x 2 mL			2 mL	3 x 2 mL (every 8 weeks)
Coagulation	2 x 2.7mL			5.4 mL	3 x 2.7 mL (every 8 weeks)
Cannabidiol	2 x 2 mL			4 mL	6 x 2 mL
PK sample (ZX008 and background AED)	--	6 x 4mL		24 mL	
AED plasma sample	--		2mL	2 mL	6 x 2 mL
Volume for flushing indwelling catheter	--	6 x 0.5mL		3 mL	
Approximate total blood volume per subject	34.4 mL	27mL	2 mL	63.4mL	122.1 mL

AED=antiepileptic drug; FSH=follicle stimulating hormone; GH=growth hormone; IGF-1=insulin-like growth factor 1; LH-luteinizing hormone; PK=pharmacokinetic

The maximum total blood volume collected during the study for Cohort 2 (clinical laboratory testing, genotyping, and PK) will be approximately 117.2 mL, as outlined in [Table 12](#).

Table 12. Estimated Blood Volume Collection for Cohort 2

Assessment	Baseline Period		Titration + Maintenance Period				Visit 13 Day 120	Total
	Screening (Day -42 to -41)	Random- ization Day -1	Day 22	Day 50	Day 78	Day 106		
Clinical chemistry, prolactin	5 mL	5 mL	5 mL	5 mL	5 mL	5 mL		42 mL
LH, FSH, estradiol, testosterone	2 mL	2 mL	2 mL	2 mL	2 mL	2 mL	--	
Hematology	2 mL	2 mL	2 mL	2 mL	2 mL	2 mL	--	12 mL
Epilepsy Genotyping	5 mL	--	--	--	--	--	--	5 mL
IGF-1 and GH	2 mL	2 mL	2 mL	2 mL	2 mL	2 mL	--	12 mL
Coagulation	2.7 mL	2.7 mL	2.7 mL	2.7 mL	2.7 mL	2.7 mL	--	16.2 mL
Cannabidiol	2 mL	2 mL	2 mL	2 mL	2 mL	2 mL	--	12 mL
ZX008 PK sample	--	--			--	--	4 x 2 mL	8 mL
AED plasma sample		1 x 2 mL	1 x 2 mL	1 x 2 mL	--	1 x 2 mL		8 mL
Volume for flushing indwelling catheter	--	--	--	--	--	--	4 x 0.5 mL	2 mL
Approximate total blood volume per subject	20.7 mL	17.7 mL	17.7 mL	17.7 mL	15.7 mL	17.7 mL	10 mL	117.2 mL

AED=antiepileptic drug; FSH=follicle stimulating hormone; GH=growth hormone; IGF-1=insulin-like growth factor 1; LH=luteinizing hormone; PK=pharmacokinetics

In concordance with The Seattle Children's Research Foundation Guidance (Appendix 9), blood collection volumes for children weighing up to 15 kg will be:

- the maximum allowable volume of blood in one draw is 22-30 mL (2.5% of total blood volume)
- the maximum in a 30-day period is 44-60 mL

On Day 120/Visit 13 the PK blood draw will be completed as the priority and the blood draw for chemistry and hematology will be skipped for those subjects who weigh less than 13.5 kg, unless medical concerns (for example, from previous tests or reported side effects) prioritize chemistry and/or hematology.

If blood collection is restricted due to volume or due to inability to draw adequate volume, collection should be prioritized as shown in [Table 13](#).

Table 13: Priorities for Blood Sample Collections

Assessment	Priority
ZX008 PK sample	Priority 1
Clinical chemistry	Priority 2
Cannabidiol	Priority 2
AED plasma sample	Priority 2
LH, FSH, estradiol, testosterone, GH, prolactin	Priority 3
Hematology	Priority 3
IGF-1	Priority 4
Genotyping	One time collection any time during or after screening
Coagulation	One time collection any time before PK day

AED = antiepileptic drug; FSH=follicle stimulating hormone; GH=growth hormone; IGF-1=insulin-like growth factor 1;
LH = luteinizing hormone; PK=pharmacokinetics

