A third recent analysis was conducted that included 7 additional patients (5 males and 2 females) who were enrolled after 2010, with data through March 2015 ([Ceulemans 2015](#)). The median starting fenfluramine dose was 10 mg per day. Mean treatment duration was 22 months. The mean seizure frequency in these 7 patients prior to initiation of fenfluramine was 11.4 per month (range 0.4 to 39.7) and at 6 months after starting fenfluramine there was a dramatic decrease with a mean of 2.6 seizures per month (range 0–6) seizures per month. Every patient's echocardiographic examinations which were normal at baseline, continued to be normal at every post-treatment assessment without any signs of valvulopathy, pulmonary hypertension or any other cardiovascular abnormality.

The dramatic long-term prospective effectiveness data described above of the Belgian cohort of Dravet syndrome patients who have now been successfully treated with fenfluramine, in some cases, for over 25 years, without any signs of clinically significant valvulopathy or reports of

pulmonary hypertension, strongly supports the potential benefit outweighs the risk in this particular patient population.

The approximate volume of blood (63.4 mL) planned for collection from Cohort 1 up to Day 15 presents no undue risk to the subjects, and will provide useful information on the PK profile of these antiepileptic medications when ZX008 is added to treatment with CLB + VPA or with CLB + VPA + STP. As noted above, the dose of ZX008 to be used in Cohort 1 will be at the low end of the dose range for subjects who are receiving STP/VPA/CLB to minimize potential side effects associated with the combination.

The 0.5 mg/kg/day, with a maximum 20 mg/day dose of ZX008 to be administered for Cohort 2 has been informed by assessment of PK and safety data derived from Cohort 1. The Independent Data and Safety Monitoring Committee (IDSMC) has been provided with the safety and PK data from Cohort 1 and have validated the methodology for the 0.5 mg/kg/day dose selected for Cohort 2. Based on previous work with ZX008 in this population, fenfluramine should provide sufficient anti-epileptic support for a sustained period of time during the study.

The safety monitoring practices employed by this protocol, including extensive cardiovascular monitoring, are adequate to protect the subjects' safety and should detect expected and unexpected treatment-emergent adverse events.

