6.1 COHORT 1: STUDY PROCEDURES

6.1.1 Screening (Up to 14 days prior to dosing)

Screening is the predetermined series of procedures with which each investigator selects an appropriate and representative sample of subjects for enrollment into the study. Subjects will attend the clinical unit for a screening visit up to 14 days prior to dosing. The screening period may be extended to ensure all screening results are reviewed for eligibility prior to dosing. Select screening data will be entered into the eCRF.

Written informed parental or guardian consent and assent of minors (if the subject is capable of providing assent) must be obtained before a subject can start any of the screening procedures. The procedure(s) for obtaining written informed consent and assent of minor (if the subject is capable of providing assent) are described in [Section 11.2](#).

The following procedures will be performed during the Screening visit, which may be split into two visits:

- Obtain written informed consent for the study
- Review inclusion and exclusion criteria
- Record demographic information
- Record medical, neurological, and epilepsy history

- Record current epilepsy status (number/type/duration seizures per month)
- Record prior medications
- Complete physical examination, including height, weight, and calculation of BMI
- Complete neurological examination
- 12-lead electrocardiogram
- Doppler ECHO
- Vital signs (blood pressure, heart rate, temperature, and respiratory rate)
- Urine pregnancy test for females of child-bearing potential
- Laboratory evaluation (serum chemistry, hematology, urinalysis, tests of growth and precocious puberty, coagulation)
- Urine THC panel
- Whole blood CBD
- Obtain blood sample for epilepsy genotype panel
- Obtain buccal swab for CYP2D6 genotype/phenotype characterization.

Only eligible subjects as specified by the inclusion and exclusion criteria with an independently confirmed diagnosis of Dravet syndrome by the Epilepsy Study Consortium will be enrolled into the study.

After enrollment into the study, each subject will be issued a “Subject Card” containing information about the subject’s participation in the study. The subject or parent/caregiver will be advised to retain this card on his person for the entire duration of the study so that the investigator or the Sponsor can be contacted in case of emergency.

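### Protocol 6.3 contradicts itself for Cohort 1: Table 11 schedules up to 63.4 mL of blood within 29 days, above the section's own 30-day limit for children up to 15 kg

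*Protocol*

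**What the plan says.** Four places in the protocol bear on this.

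- **The planned volume.** Section 6.3 states: "The maximum total blood volume collected during the first 15 days of the study for Cohort 1 will be approximately 63.4 mL". Table 11 builds the figure from three columns: one headed "Screening (Day -14 to -1" (34.4 mL), Day 1-2 (27 mL) and Day 15 (2 mL). They are added under "Total Screening- Day 15". The table's total therefore starts at screening, although the sentence describes the first 15 days. Section 6.1.1 sets the screening interval: "Subjects will attend the clinical unit for a screening visit up to 14 days prior to dosing".
- **The limit.** Section 6.3 then introduces weight-specific ceilings with "blood collection volumes for children weighing up to 15 kg will be", and the second of these reads: "the maximum in a 30-day period is 44-60 mL". Appendix 9 is the cited source, and the range is its 11 to 15 kg row.
- **The fallback.** Table 13 ranks the samples for use when volume has to be restricted. PK is Priority 1. Chemistry, cannabidiol and AED plasma are Priority 2. Hormones and hematology are Priority 3, and IGF-1 is Priority 4. Genotyping is a single sample at any time during or after screening, and coagulation a single sample before the PK day. Table 11 has coagulation twice, at 2 x 2.7 mL. The only explicit weight-based omission (below 13.5 kg) is for Day 120/Visit 13, which is a Cohort 2 visit.
- **The risk statement.** Section 1.6 says: "The approximate volume of blood (63.4 mL) planned for collection from Cohort 1 up to Day 15 presents no undue risk to the subjects". It has no exception by weight.

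Section 4.1 admits children from age 2 and sets no minimum weight.

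**The concern.** The limit is a paediatric safety ceiling that the protocol sets for itself, and one of its own schedules does not fit under it. A site with a 12 kg child in Cohort 1 finds two instructions in one section: a table of samples adding up to 63.4 mL, and a ceiling of 48 mL at that weight. It is not told that the routine schedule already exceeds the ceiling, at what weight this starts, or which tubes to leave out. An ethics committee reading Section 1.6 would take the no-undue-risk statement to cover every eligible child, including those for whom the scheduled volume is above the protocol's own limit.

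The PK data are also at stake. If samples give way without a plan, those lost may be the PK samples for which Cohort 1 exists, because they are drawn last.

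**Working it through.** **Step 1. Reproduce the plan's figure (Table 11).**

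- Screening to Day -1: chemistry and prolactin 10 + LH/FSH/estradiol/testosterone 4 + hematology 4 + genotyping 5 + IGF-1/GH 2 + coagulation 5.4 + cannabidiol 4 = 34.4 mL.
- Day 1-2: PK 6 x 4 = 24, plus catheter discard 6 x 0.5 = 3, giving 27 mL.
- Day 15: AED plasma 2 mL.
- Total: 34.4 + 27 + 2 = 63.4 mL, an exact match.

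**Step 2. The window.** Day -14 to Day -1 is 14 days and Day 1 to Day 15 is 15 days (no Day 0), so 29 days. With the ±1 day allowance on Day 15 it is at most 30. On the standard schedule the whole amount falls in one 30-day period.

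**Step 3. The limit as a function of weight (Appendix 9).** Total blood volume is taken as 80 mL/kg. At 11 kg the limit is 44/880 = 5% of it, and at 15 kg it is 60/1200 = 5%. So limit = 0.05 x 80 x weight = 4 mL/kg per 30 days.

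**Step 4. Excess if every Table 11 sample is drawn.**

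| Weight (kg) | Limit (mL) | 63.4 minus limit (mL) | Excess over limit |
|---|---|---|---|
| 11 | 44 | 19.4 | 44% |
| 12 | 48 | 15.4 | 32% |
| 13 | 52 | 11.4 | 22% |
| 14 | 56 | 7.4 | 13% |
| 15 | 60 | 3.4 | 6% |
| 16 | 64 | -0.6 | fits |

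Break-even is 63.4/4 = 15.85 kg. Below 11 kg the Appendix 9 limit falls further: 40 mL at 10 kg, an excess of 23.4 mL. Leaving out the 3 mL catheter discard gives 60.4 mL, still above 60.

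**Step 5. What Table 13 can remove.**

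| Cumulative step | Remaining (mL) | Fits from (remaining/4, kg) |
|---|---|---|
| Defer genotyping (-5) | 58.4 | 14.6 |
| Coagulation once (-2.7) | 55.7 | 13.9 |
| Drop separately listed Priority 3-4 tubes (-4 -4 -2) | 45.7 | 11.4 |
| Drop coagulation altogether (-2.7) | 43.0 | 10.75 |

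The two steps that lose no assay leave 55.7 mL, above the limit at 11, 12 and 13 kg. Reaching 44 mL at 11 kg means dropping hematology, the separately drawn hormones, IGF-1 and coagulation.

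**Step 6. Order of the draws.** Of the non-PK blood, 34.4 mL is scheduled before Day 1 and only 2 mL after. If all 34.4 mL has been drawn by Day -1, the allowance left is 44 - 34.4 = 9.6 mL at 11 kg, 52 - 34.4 = 17.6 mL at 13 kg and 60 - 34.4 = 25.6 mL at 15 kg. The PK days need 27 mL. The Table 13 order therefore protects the PK samples only if the cuts are made before dosing.

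**Step 7. Sensitivity to the window.** Section 6.1.1 lets screening be extended. Assume that one of each paired sample, and every single sample, is taken at the screening visit: 5 + 4 + 2 + 5 + 2 + 2.7 + 2 = 22.7 mL. If that visit falls outside the 30 days, what remains is 63.4 - 22.7 = 40.7 mL, which fits at 11 kg. A screening interval shorter than 14 days keeps everything inside the window.

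**The case against.** The strongest reply is that Section 6.3 already handles the conflict. The 63.4 mL is described as an approximate maximum and is not tied to weight. The ceiling for children up to 15 kg follows in the same section and is not confined to Cohort 2. Table 13 then says what goes first when volume is restricted. Read together, the ceiling overrides the table, and sites can comply by deferring genotyping and dropping lower-ranked tubes.

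Much of this stands. A reader might infer that the plan breaks the limit for every child of 15 kg or less, or that nothing requires a cut. The documents support neither. A site that applies the ceiling and Table 13 can stay within it at most weights in the band (Step 5), and an extended screening period can have the same effect (Step 7). What the reply does not supply is a statement that the routine Cohort 1 schedule triggers the restriction, the weight at which it does so, or a sequence in which the cuts come before the PK draws. Nor does it explain why coagulation is one-time in Table 13 and twice in Table 11, or why Section 1.6 is unqualified.

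A second reply is that few children are still affected. This also has force. Section 3.5 reports data from 13 Cohort 1 subjects, 10 of them in Regimen 3, whose planned number is 10. Against the target of 18-20, that leaves 5 to 7. The text is also labelled a US/Canada amendment, whereas Cohort 1 enrols in France and the Netherlands. Versions for those countries are not available here, so their wording cannot be checked.

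**Conclusion.** The contradiction is real. On the standard 29-day schedule, with every Table 11 sample drawn, the planned 63.4 mL exceeds the protocol's own 30-day limit throughout the 11 to 15 kg band, by 3.4 mL (6%) at the top and 19.4 mL (44%) at the bottom. The full schedule first fits at about 15.9 kg. Table 13 softens this but does not resolve it.

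The figures rest on two assumptions: that screening is at most 14 days before dosing, and that Appendix 9 is applied at 4 mL/kg.

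A reader might also infer that many Cohort 1 children are affected, since each regimen reserves places for under-6s. The documents give no weights for these children and no count at or below 15 kg, so the number affected is unknown. Nor can Regimen 3 be presented as a group still to be exposed, since its planned number already had data. The finding concerns inconsistent protocol text. It does not show that any child was over-sampled, and it does not determine which volume is correct.

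**What to change.** Reconcile four places for Cohort 1 children up to 15 kg: Table 11, the Section 6.3/Appendix 9 limit, Table 13 and the Section 1.6 risk statement. After reconciliation they should agree on:

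- the planned volume by weight, and the window it covers (first 15 days, or screening to Day 15);
- whether and at what weight the routine schedule triggers the Table 13 order, and which samples give way, settled before the Day 1 PK draws;
- whether coagulation is drawn once or twice;
- the scope of the no-undue-risk statement.

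Which volume governs is for the sponsor and its clinical advisers to decide. The cost is protocol wording. Some lower-priority samples may be missed in the smallest children, and planning this in advance would make the gaps predictable.
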